### **6.1 Management of toxicities attributable to atezolizumab**

Toxicities associated or possibly associated with atezolizumab treatment should be managed according to standard medical practice. Additional tests, such as autoimmune serology or biopsies, may be used to determine a possible immunogenic etiology.

Although most immune-related adverse events (irAEs) observed with immunomodulatory agents have been mild and self-limiting, such events should be recognized early and treated promptly to avoid potential major complications. Discontinuation of atezolizumab may not have an immediate therapeutic effect and, in severe cases, immune-related toxicities may require acute

management with topical corticosteroids, systemic corticosteroids, mycophenolate, or TNF $\alpha$  inhibitors.

The primary approach to Grade 1 to 2 irAEs is supportive and symptomatic care with continued treatment with atezolizumab; for higher-grade irAEs, atezolizumab should be withheld and oral and/or parenteral steroids administered. Recurrent Grade 2 irAEs may also mandate withholding atezolizumab or the use of steroids. Assessment of the risk-benefit ratio should be made by the investigator, with consideration of the totality of information as it pertains to the nature of the toxicity and the degree of clinical benefit a given patient may be experiencing prior to further administration of atezolizumab. Atezolizumab should be permanently discontinued in patients with life-threatening irAEs.

#### 6.1.1 Guidelines for Dosage Modification and Treatment Interruption or Discontinuation

There will be no dose reduction for atezolizumab in this study. Patients may temporarily suspend study treatment for up to 84 days beyond the scheduled date of delayed infusion if study drug-related toxicity requiring dose suspension is experienced. If atezolizumab is held because of AEs for >84 days beyond the scheduled date of infusion, the patient will be discontinued from atezolizumab and will be followed for safety and efficacy as specified in Section 5.5.

Patients should be assessed clinically for toxicity prior to, during, and after each infusion. Any toxicity associated or possibly associated with atezolizumab treatment should be managed according to standard medical practice. Additional tests, such as autoimmune serology or biopsies, may be used to determine a possible immunogenic etiology. Although most irAEs observed with immunomodulatory agents have been mild and self-limiting, such events should be recognized early and treated promptly to avoid potential major complications. Discontinuation of atezolizumab may not have an immediate therapeutic effect, and there is no available antidote for atezolizumab. In severe cases, immune-related toxicities may be acutely managed with topical corticosteroids, systemic corticosteroids, mycophenolate, or TNF $\alpha$  inhibitors.

Management of hepatitis/transaminitis, colitis, rash, and hypothyroidism are presented in this section as they have been observed in this study and are potentially immune related.

Dose interruptions for reasons other than toxicity, such as planned surgical procedures, may be allowed, with prior PI approval. The interruption should not be greater than 84 days.

##### 6.1.1.1 Gastrointestinal Toxicity

Immune-mediated colitis has been associated with the administration of atezolizumab.

Patients should be advised to inform the investigator if any diarrhea occurs, even if it is mild.

If the event is of significant duration or magnitude, or is associated with signs of systemic inflammation or acute phase reactants (e.g., increased CRP or platelet count or bandemia), it is recommended that sigmoidoscopy (or colonoscopy, if appropriate) with colonic biopsy with three to five specimens for standard paraffin block be performed. If possible, one or two biopsy specimens should be snap frozen and stored.

Treatment may be restarted following the resolution of colitis. In addition, if the patient is being managed with corticosteroids, treatment should not be restarted until the steroids have been tapered down to a prednisone dose  $\leq 10$  mg/day. Patients who resume treatment should be monitored closely for signs of renewed diarrhea. Table 1 provides a summary of dose modification guidelines for gastrointestinal toxicities.

**Table 1 Dose Modification Guidelines for Gastrointestinal Toxicity**

Toxicity	Description	Management
Diarrhea and/or Colitis	Grade 1	
 
• Continue atezolizumab.
 
• Initiate symptomatic treatment
 
• Endoscopy is recommended if symptoms persist for > 7 days
 
• Close monitoring.
 

	Grade 2	
 
• Hold atezolizumab
 
• Initiate symptomatic treatment
 
• For recurrent events or events that persist > 5 days: start Prednisone 60 mg/day or equivalent.
 
• When symptoms improve Grade <math>\leq 1</math>, resume atezolizumab               
 
○ Corticosteroids must be tapered over <math>\geq 1</math> month to <10 mg/day oral prednisone or equivalent before resuming.
 
 
 
• Atezolizumab may be resumed if the event improves to Grade <math>\leq 1</math> within 12 weeks, and corticosteroids have been reduced to the equivalent of prednisone <math>\leq 10</math> mg/day.               
 
○ Atezolizumab may be withheld for a longer period of time (i.e., >12 weeks after event onset) to allow for corticosteroids (if initiated) to be reduced to <math>\leq 10</math> mg/day oral prednisone or equivalent. The acceptable length of the extended period of time must be determined by the PI
 
 
 

	Grade 3	
 
• Hold atezolizumab.
 
• Treat with IV steroids (1-2 mg/kg/day methylprednisolone or equivalent) and convert to oral steroids (prednisone 60 mg/day or equivalent) after improvement. When symptoms improve to Grade <math>\leq 1</math>, taper steroids over <math>\geq 1</math> month               
 
○ If event resolves to <math>\geq</math> Grade 1, restart atezolizumab
 
 
 
• If event does not resolve to > grade 1 within 12 weeks of holding, permanently discontinue               
 
○ If the subject was unequivocally deriving clinical benefit, the subject may be rechallenged as
 
 
 

	
determined by the PI.
 
 
• Gastroenterology referral and confirmation biopsy
 

	
Grade 4
 
 
• Permanently discontinue atezolizumab and inform PI           
 
○ If event resolves to Grade 1 or better within 12 weeks from last dose of atezolizumab, and if the subject was unequivocally deriving clinical benefit, the subject may be able to resume Atezolizumab as determined by the PI.
 
 
 
• Gastroenterology referral and confirmation biopsy
 
• Treat with IV steroids (1–2 mg/kg/day methylprednisolone or equivalent) and convert to oral steroids (prednisone 60 mg/day or equivalent) after improvement. When symptoms improve to Grade <math>\leq</math> 1, taper steroids over <math>\geq</math> 1 month
 
• If symptoms are not improving after 48 hours of initiating steroids or are worsening, addition of an alternative immunosuppressive agent (e.g., mycophenolate or TNF-<math>\alpha</math> antagonist) may be considered.
 

IV = intravenous; TNF- $\alpha$  = tumor necrosis factor alpha.

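### Table 1, Grade 3 diarrhea/colitis: the comparison signs in the restart line and the 12-week stopping line both point the wrong way

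*Combined protocol and SAP*

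**What the plan says.** Section 6.1.1.1 presents Table 1 as the summary of dose modification for gastrointestinal toxicity. In the Grade 3 row, atezolizumab is held, intravenous steroids are given, and treatment converts to oral prednisone after improvement. A clause beginning "When symptoms improve to Grade" ≤ 1 then starts a steroid taper of at least one month. Nested under that bullet is the restart line: "If event resolves to \geq Grade 1, restart atezolizumab", where the sign is ≥.

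The next bullet is the stopping line: "If event does not resolve to > grade 1 within 12 weeks of holding, permanently discontinue". It carries an exception at the PI's discretion: "If the subject was unequivocally deriving clinical benefit, the subject may be rechallenged as" the PI decides.

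Three other provisions bear on the same decision:

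- The text of 6.1.1.1 states "Treatment may be restarted following the resolution of colitis". For patients on corticosteroids it adds that "treatment should not be restarted until the steroids have been tapered down to a prednisone dose" of 10 mg/day or less.
- Section 6.1.1 sets a general limit: "If atezolizumab is held because of AEs for >84 days beyond the scheduled date of infusion, the patient will be discontinued from atezolizumab".
- The Grade 2 row of Table 1 states "Atezolizumab may be resumed if the event improves to Grade" ≤ 1 within 12 weeks, with the same steroid condition.

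**The concern.** These two lines are the operative restart and stopping thresholds for Grade 3 colitis, and section 7.1.3.1 lists colitis as an adverse event of special interest. With the printed signs, full recovery fails the restart condition and satisfies the stopping condition, while an event that remains severe does the opposite.

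A site that follows the row literally could withdraw a recovered patient from therapy. A site that does the sensible thing departs from the printed rule, and the departure could be queried as a deviation.

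**Working it through.** The plan gives no figure to reproduce here. The check is logical: evaluate each line for each residual grade, then compare with the surrounding rules.

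**Inputs (Table 1, Grade 3 row).**
- Restart as printed: grade ≥ 1.
- Permanent discontinuation as printed: at 12 weeks, not (grade > 1), which is the same as grade ≤ 1.
- Corrected condition for both lines: Grade ≤ 1 restarts; not (Grade ≤ 1) at 12 weeks discontinues.

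| Residual grade | Restart line as printed | Stopping line as printed, week 12 | With Grade ≤ 1 in both lines |
|---|---|---|---|
| 0 | not met | met: discontinue | restart |
| 1 | met: restart | met: discontinue | restart |
| 2 | met: restart | not met | discontinue at week 12 |
| 3 | met: restart | not met | discontinue at week 12 |

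The printed lines give the wrong result at Grade 0 and contradict each other at Grade 1 if the patient is still held at week 12. At Grade 2 and above both point the wrong way. The corrected lines are complementary at every grade.

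**Other text that governs the same patient.**
- At residual Grade 2, the restart line sits under a bullet that takes effect only at Grade ≤ 1. Section 6.1.1.1 requires resolution of colitis and prednisone at or below 10 mg/day. Restart is therefore blocked.
- A prolonged hold at Grade 2 is ended by section 6.1.1: 84 days / 7 = 12 weeks beyond the scheduled infusion. Residual Grade 2 is therefore not counted as a failure.
- At Grade 0, section 6.1.1.1 permits restart, so it conflicts directly with the Table 1 line.

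**Parallel rules.** All run opposite to the printed signs:
- Table 1, Grade 2 row: resume at Grade ≤ 1.
- Table 1, Grade 4 row: possible resumption once the event is down to Grade 1 or lower within 12 weeks.
- Table 3, Grade 3 rash: discontinue if the event has not come down to Grade 1 or lower.
- Table 5, Grade 2 pneumonitis, and Table 6, Grade 2 eye toxicity: the same threshold, with a 12-week limit.

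No text in the document supports the literal signs.

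**Could it be a PDF reading error?** It is unlikely. In the same row, Grade ≤ 1 and the taper of ≥ 1 month read sensibly. The two faulty lines carry different symbols (≥ and >), so two separate signs would have had to be corrupted in the same direction.

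**The case against.** The strongest reply accepts that the signs are wrong and disputes the consequence.

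1. **Intent is recoverable.** Resolving from Grade 3 implies improvement, so a clinician may read the restart line as meaning at least down to Grade 1. Few investigators would stop a drug because colitis had cleared. This stands as a limit on harm. It does not defend the wording, since the protocol spells out the Grade 1 threshold in words elsewhere.
2. **Section 6.1.1.1 rescues Grade 0 just as other text rescues Grade 2.** This stands in part. That section is permissive about restart, whereas the Table 1 stopping line is an instruction. The two conflict, and neither is said to prevail.
3. **The bullet above the restart line is a steroid-taper trigger, not a stated restart condition.** This is fair. The firmer barrier at Grade 2 is section 6.1.1.1.
4. **Few recovered patients would still be held at week 12, and section 6.1.1 ends holds beyond 84 days anyway.** The window is indeed narrow. However, Grade 3 management requires a taper of at least a month to 10 mg/day or less, and the Grade 2 row itself foresees holds beyond 12 weeks for this reason. At Grade 0 the restart line also fails before week 12.
5. **Reach is small.** Section 2.3.2.2 names the most frequent related Grade ≥ 3 events among 412 single-agent patients down to 3 patients (0.7%), and colitis is not among those named. If its rate were no higher than 3/412, 45 patients would give at most 45 × 3/412 ≈ 0.33 expected cases. That list may be incomplete and excludes radiation combinations, so this is an illustration under an assumption.
6. **Reversing > strictly gives < Grade 1, meaning Grade 0 only.** This is correct. The second sign has to be replaced by ≤.

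**Conclusion.** The point holds: the Grade 3 row is wrong as written. The clear failures are a patient at Grade 0, who is refused restart and then discontinued, and a patient at Grade 1 still held at week 12, who receives two opposite instructions. Residual Grade 2 is excluded because other text covers it.

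Severity is low. The section text, the 84-day limit and the PI exception contain most of the practical risk, and no endpoint, sample size or analysis depends on these lines. It is still an error in a dosing threshold for an event of special interest, and should be corrected. The conclusion assumes that the signs in the source file match the text reviewed. The documents do not give the frequency of Grade 3 colitis in this trial.

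**What to change.** Check the two signs against the source file, then edit the Grade 3 row of Table 1:

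1. In the restart line, replace ≥ Grade 1 with Grade ≤ 1. The steroid condition in 6.1.1.1 already applies and may be cross-referenced.
2. In the 12-week stopping line, replace > grade 1 with Grade ≤ 1, so that failure to reach Grade ≤ 1 leads to permanent discontinuation. Do not use < grade 1.
3. Keep the PI rechallenge exception and leave the 84-day limit in 6.1.1 unchanged.

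The cost is two signs in one table row, which can go into the next protocol amendment. Data collection and analysis are unaffected.

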### 6.1.1.2 Hepatotoxicity

Immune-mediated hepatitis has been associated with the administration of atezolizumab.

While in this study, patients presenting with right upper-quadrant abdominal pain and/or unexplained nausea or vomiting should have LFTs performed immediately, and LFTs should be reviewed before administration of the next dose of study drug.

If LFTs increase, neoplastic, concurrent medications, viral hepatitis, and toxic etiologies should be considered and addressed, as appropriate. Imaging of the liver, gall bladder, and biliary tree should be performed to rule out neoplastic or other causes of increased LFTs. Anti-nuclear antibody, perinuclear anti-neutrophil cytoplasmic antibody, anti-liver kidney microsomal, and anti-smooth muscle antibody tests should be performed if an autoimmune etiology is considered.

Patients with LFT abnormalities should be managed according to the guidelines in Table 2. For patients with elevated LFTs at baseline (between 3-5 x ULN) due to documented liver metastases, further elevation of LFTs may not require dose interruptions if the ALT and/or AST have risen < 3 x baseline value and if the total bilirubin elevation remains < 2x ULN with normal PT/INR. Such cases should be also discussed with the principal investigator.

**Table 2 Dose Modification Guidelines for Hepatotoxicity**

Toxicity	Description	Management
LFT and/or total bilirubin abnormalities	Grade 1	
 
Continue Atezolizumab and monitor labs according to study calendar
 

	Grade 2	
 
Continue Atezolizumab and monitor LFTs more frequently until return to baseline or Grade ≤1
 
If persistent > 5 days, hold atezolizumab, and start prednisone 60 mg/day or equivalent. When LFTs improve to Grade ≤1 taper steroids over ≥1 month
 
When LFTs improve to Grade ≤1 and the steroid dose is prednisone ≤ 10 mg/day or equivalent (if initiated), restart atezolizumab
 

	Grade 3 or 4	
 
Permanently discontinue atezolizumab, start prednisone 60 mg/day or equivalent and inform the PI               
 
If the subject was unequivocally deriving clinical benefit, the subject may be able to resume Atezolizumab as determined by the PI.
 
 
 
If LFT results do not decrease within 48 hours after initiation of systemic steroids, consider addition of an alternative immunosuppressive agent (e.g., mycophenolate) to the corticosteroid regimen
 
Consider obtaining a hepatology consult and liver biopsy.
 
 When LFTs improve to Grade ≤1 taper steroids over ≥1 month

---

IV=intravenous; LFT=liver function test; TNF $\alpha$ =tumor necrosis factor alpha; ULN=upper limit of normal.

### 6.1.1.3 Dermatologic Toxicity

Treatment-emergent rash has been associated with atezolizumab. The majority of cases of rash were mild in severity, self-limited, both with and without pruritus. Low-grade rash and pruritus irAEs have been treated with symptomatic therapy (e.g., antihistamines). Topical or parenteral corticosteroids may be required for more severe symptoms. A dermatologist should evaluate persistent and/or severe rash or pruritus and consider biopsying the site.

Dermatologic toxicity and rash should be managed according to the guidelines in Table 3.

**Table 3 Dose Modification Guidelines for Dermatologic Toxicity**

Toxicity	Description	Management
Dermatologic toxicity/rash (e.g., maculopapular or purpura)	Grade 1: Mild < 10% BSA	
 
• Continue atezolizumab
 
• Consider topical steroids and/or other symptomatic therapy (e.g., antihistamines).
 

	Grade 2: Moderate 10%–30% BSA	
 
• Continue atezolizumab.
 
• Administer topical steroids and consider higher potency topical steroids if events do not improve
 
• Consider dermatologist referral.
 

	Grade 3: Severe >30% BSA	
 
• Hold atezolizumab and administer oral prednisone 10 mg or equivalent.
 
• If the rash is not improved after 48–72 hours, increase oral dose of prednisone to 60 mg or equivalent.
 
• Refer for dermatology consult.
 
• Restart atezolizumab if rash is resolved to grade 1 or better and systemic dose is ≤ 10 mg oral prednisone equivalent per day (taper over 1 month).
 
• If event does not resolve to Grade 1 or better while withholding atezolizumab, permanently discontinue atezolizumab and contact PI               
 
• If the subject was unequivocally deriving clinical benefit, the subject may be able to resume atezolizumab as determined by the PI.
 
 
 

	Grade 4	
 
• Permanently discontinue atezolizumab and inform the PI
 
• If the subject was unequivocally deriving clinical benefit, the subject may be able to resume atezolizumab as determined by the PI
 

BSA=body surface area; PRN=as needed.

#### 6.1.1.4 Endocrine Toxicity

Hypothyroidism has been associated with the administration of atezolizumab.

Patients with unexplained symptoms such as fatigue, myalgias, impotence, mental status changes, or constipation should be investigated for the presence of hyponatremia, hypokalemia and thyroid, pituitary and adrenal endocrinopathies. An endocrinologist should be consulted if an endocrinopathy is suspected.

Hypophysitis is a rare condition, characterized by the development of hypopituitarism with multiple anterior pituitary hormone deficiencies (e.g., low levels of adrenocorticotropic hormone (ACTH), thyroid-stimulating hormone (TSH).) MRI typically reveals a diffuse enlargement of the pituitary gland.

Cases of hypophysitis have been reported in patients receiving Atezolizumab. Among 2,616 patients treated with single agent Atezolizumab in clinical trials, hypophysitis occurred in 2 patients. It is recommended that Atezolizumab be withheld for grade 2 or grade 3 hypophysitis

and permanently discontinued for grade 4 events. Corticosteroids and hormone replacement therapy should be administered at the discretion of the treating physician.

**Table 4 Dose Modification Guidelines for Endocrine Toxicity**

Toxicity	Management
Asymptomatic Hypothyroidism	
 
• Continue atezolizumab
 
• Start treatment with thyroid replacement hormone
 
• Monitor thyroid-stimulating hormone (TSH) weekly
 

Symptomatic Hypothyroidism	
 
• Hold atezolizumab
 
• Start treatment with thyroid replacement hormone
 
• Monitor TSH weekly
 
• Consider referral to an endocrinologist
 
• Restart atezolizumab when symptoms are controlled
 

Asymptomatic Hyperthyroidism	
 
• If serum TSH < 0.5 mU/L and >0.1 mU/L, continue atezolizumab and monitor TSH every 4 weeks.
 
• If serum TSH < 0.1 mU/L, follow guidelines for symptomatic hyperthyroidism.
 

Symptomatic Hyperthyroidism	
 
• Hold atezolizumab
 
• Initiate treatment with anti-thyroid drug such as methimazole as needed
 
• Consider referral to an endocrinologist
 
• If symptoms are controlled and thyroid function is improving, resume atezolizumab
 
• Permanently discontinue atezolizumab for life-threatening immune-related hyperthyroidism. Inform PI and CRC.
 

Hyperglycemia, grade 1-2	
 
• Continue atezolizumab.
 
• Initiate treatment if clinically indicated
 
• Monitor for glucose control.
 

Hyperglycemia, grade 3-4	
 
• Hold Atezolizumab
 
• Initiate treatment for hyperglycemia
 
• Monitor for glucose control.
 
• Resume atezolizumab when symptoms resolve and glucose levels are stable.
 

Hypophysitis any grade 2 or 3 events	
 
• Hold atezolizumab until toxicity improve to Grade <math>\leq</math> 1
 
• Corticosteroids and hormone replacement therapy should be administered as clinically indicated.
 
• Consult an endocrinologist
 
• If toxicity does not resolve within 12 weeks of last dose or inability to reduce corticosteroid to 10 mg or less of prednisone or equivalent per day within 12 weeks, permanently discontinue atezolizumab. Inform PI and study team.
 
• For recurrent hypophysitis, treat as Grade 4.
 

Hypophysitis grade 4	

• Permanently discontinue atezolizumab and treat with an initial dose of methylprednisolone 1 to 2 mg/kg per day intravenously followed by oral prednisone 1 to 2 mg/kg per day upon improvement. Inform PI

• When symptoms improve to Grade <math>\leq 1</math>, start steroid taper and taper over <math>\geq 1</math> month, resume atezolizumab

• Consult an endocrinologist

• Perform appropriate imaging

• Initiate hormone replacement therapy, if clinically indicated

• If event does not resolve to Grade 1 or better while withholding atezolizumab, permanently discontinue atezolizumab and contact PI

• If the subject was unequivocally deriving clinical benefit, the subject may be able to resume Atezolizumab as determined by the PI.

----------------------	--

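### Table 4, Grade 4 hypophysitis: the row orders permanent discontinuation and then tells the investigator to resume atezolizumab

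*Combined protocol and SAP*

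**What the plan says.** The Grade 4 hypophysitis row of Table 4 (Section 6.1.1.4) contains four instructions that bear on re-dosing:

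- Bullet 1: "Permanently discontinue atezolizumab and treat with an initial dose of methylprednisolone". It also requires that the PI be informed.
- Bullet 2: once symptoms improve to Grade 1 or lower, taper steroids over at least a month; it ends "month, resume atezolizumab".
- A later bullet: "If event does not resolve to Grade 1 or better while withholding atezolizumab, permanently discontinue atezolizumab and contact PI".
- A sub-bullet beneath that one: "If the subject was unequivocally deriving clinical benefit, the subject may be able to resume Atezolizumab as determined by the PI".

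Outside the row, Section 6.1 states: "Atezolizumab should be permanently discontinued in patients with life-threatening irAEs". The text of Section 6.1.1.4 says hypophysitis should lead to a hold at Grade 2 or 3 "and permanently discontinued for grade 4 events". The Grade 2 or 3 row of Table 4 directs that recurrent hypophysitis be handled as Grade 4, so those patients come under this row too.

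**The concern.** A drug cannot be permanently stopped, resumed on recovery, and stopped only if recovery fails. Two investigators with the same patient could reach opposite decisions and each cite the protocol.

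Read literally, bullet 2 lets a recovered patient restart with no PI determination, no requirement of unequivocal benefit and no steroid-dose ceiling. The PI exception sits under an event that has not resolved, so it does not govern the recovered patient whom bullet 2 addresses. At stake is re-exposure after a life-threatening or recurrent immune-related event without the safeguards that the protocol applies to comparable events.

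**Working it through.** The protocol has no figure of its own to reproduce here. The check compares texts and then sizes the problem.

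**1. Which instruction is intended.** Bullet 1, Section 6.1 and the text of Section 6.1.1.4 all say permanent discontinuation. The sentence about non-resolution during a hold also appears in the Grade 3 rash row of Table 3. That row begins by holding the drug, so the sentence makes sense there. In a row that begins with a permanent stop, it does not.

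**2. Comparison with other rows.** Five other rows order permanent discontinuation at Grade 4 (or Grade 3-4) and still permit restart:

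| Row | Unequivocal benefit | PI determination | Resolution to Grade 1 or better within 12 weeks |
|---|---|---|---|
| Table 1, colitis Grade 4 | yes | yes | yes |
| Table 2, hepatic Grade 3 or 4 | yes | yes | no |
| Table 3, rash Grade 4 | yes | yes | no |
| Table 5, pneumonitis Grade 3-4 | yes | yes | yes |
| Table 6, eye Grade 3-4 | yes | yes | no |
| Table 4, hypophysitis Grade 4, bullet 2 | no | no | Grade 1 or lower, no time limit |

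Benefit and PI determination are required in 5 of 5 comparators; the 12-week condition is required in 2 of 5.

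**3. Comparison with the less severe row.** The Grade 2 or 3 hypophysitis row orders permanent discontinuation if steroids cannot be brought to 10 mg/day of prednisone or less within 12 weeks. Bullet 2 of the Grade 4 row requires a taper but names no dose. On this point the more severe row is the looser one.

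**4. Routes to restart.**

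- Now: (a) improvement to Grade 1 or lower plus taper, with no PI decision or benefit test; (b) an unresolved event plus benefit plus PI determination.
- After the change below: one route, benefit plus PI determination. It is stricter for recovered patients and no looser for unresolved ones.

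**5. Frequency.** Section 6.1.1.4 gives 2 cases of hypophysitis among 2,616 single-agent patients; the target enrolment is 45.

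- Rate: 2/2,616 = 0.0765%; exact (Clopper-Pearson) 95% interval 0.0093% to 0.2759%.
- Expected cases: 45 × 2/2,616 = 0.034 (0.0042 to 0.124 over the interval).
- Chance of at least one: 1 − (1 − 2/2,616)^45 = 3.4% (0.42% to 11.7%).
- Chance of none: 100% − 3.4% = 96.6%.

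These figures cover all grades. Only Grade 4 or recurrent cases reach this row, so the number affected is smaller. The documents give no split by grade.

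**The case against.** The case for leaving this as a minor wording matter has several parts.

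*Other controls exist.* Section 6.1 says "Assessment of the risk-benefit ratio should be made by the investigator" before further dosing. Section 6.1.1 adds: "If atezolizumab is held because of AEs for >84 days beyond the scheduled date of infusion, the patient will be discontinued from atezolizumab". Section 5.5 requires immediate notice to the overall PI of life-threatening complications, and Section 7.4 requires serious events to reach the PI within one business day. Hypophysitis is an adverse event of special interest with its own expedited report (Sections 7.1.3.1 and 7.5). This stands as far as it goes: the PI would know of the event before any restart. But notification is not determination, and none of these provisions settles which bullet applies.

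*The comparator count is selective.* Grade 3-4 hyperglycemia in Table 4 and the ungraded symptomatic row in Table 6 allow restart without the PI. That is true, but neither orders permanent discontinuation at Grade 4, so neither contains this contradiction.

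*The nesting is usual.* A PI exception under an unresolved event also appears at Grade 3 colitis, Grade 3 rash, Grade 2 pneumonitis and Grade 2 eye toxicity. This also stands, but those are rows in which the drug is held. The fault here is that hold wording sits in a row that stops the drug.

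*The repair adds no steroid ceiling or recovery condition, and Sections 6.1 and 6.1.1.4 mention no PI exception.* Both observations are correct. The repair does remove the one route that allowed restart without PI determination. The exception that remains has no recovery or steroid condition today either.

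**Conclusion.** The concern holds. The Grade 4 hypophysitis row is wrong as written, and the intended rule, permanent discontinuation, is clear from bullet 1 and Sections 6.1 and 6.1.1.4. It should be corrected because it is a safety dosing rule and the repair is trivial, although it will probably never be invoked in a trial of this size. The frequency estimate assumes that the single-agent rate carries over; the documents give no rate for atezolizumab combined with cranial radiation. The conclusion that the row contradicts itself does not depend on that assumption.

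**What to change.** In the Grade 4 hypophysitis row of Table 4:

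1. Delete the instruction to resume atezolizumab from bullet 2 and keep the steroid taper.
2. Delete the bullet that makes permanent discontinuation depend on non-resolution during a hold.
3. Move the PI exception, wording unchanged, directly under bullet 1. The row then has one default and one exception, as in the Grade 4 provisions of Tables 2, 3 and 6.

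Two optional additions are for the sponsor's clinical judgement and are not needed to remove the contradiction. One is a recovery condition: resolution to Grade 1 or better within 12 weeks, as in Tables 1 and 5, or the 10 mg/day steroid ceiling from the Grade 2 or 3 hypophysitis row. The other is a short cross-reference in Sections 6.1 and 6.1.1.4 to the PI exceptions in the tables.

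The cost is two deletions and one move in a single table row, made with the next amendment; a stand-alone amendment is not warranted. Visits and data collection do not change.

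### The Grade 4 hypophysitis cell of Table 4 orders both a permanent stop and a restart of atezolizumab; the restart contradicts the Section 6.1.1.4 text

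*Combined protocol and SAP*

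**What the plan says.** Table 4 in protocol Section 6.1.1.4 has one row for Grade 2 or 3 hypophysitis and one for Grade 4. The parts of the Grade 4 cell that matter are these:

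- First bullet: "Permanently discontinue atezolizumab and treat with an initial dose of methylprednisolone 1 to 2 mg/kg per day intravenously", then oral steroids on improvement, and notification of the PI.
- Second bullet: on improvement to Grade 1 or better, taper steroids over at least a month, ending "month, resume atezolizumab".
- Last bullet: "If event does not resolve to Grade 1 or better while withholding atezolizumab, permanently discontinue atezolizumab and contact PI". A sub-bullet lets the PI allow resumption if the patient was clearly benefiting.

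The remaining bullets cover an endocrinology consult, imaging and hormone replacement.

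The text of Section 6.1.1.4 recommends withholding for Grade 2 or 3 hypophysitis, "and permanently discontinued for grade 4 events". It gives no exception. It also reports that among 2,616 patients on single-agent atezolizumab, "hypophysitis occurred in 2 patients".

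The Grade 2 or 3 row of Table 4 adds two rules. One is "For recurrent hypophysitis, treat as Grade 4". The other ends treatment if the event has not resolved within 12 weeks of the last dose, or on "inability to reduce corticosteroid to 10 mg or less of prednisone or equivalent per day within 12 weeks, permanently discontinue atezolizumab".

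**The concern.** A permanent stop and an instruction to restart cannot both apply to the same patient. Section 6 says dose changes follow the tables, which would normally settle a difference between text and table. It cannot help here because both orders sit in one table cell.

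At stake is whether a patient who has had Grade 4 or recurrent hypophysitis is given the drug again. Restart from this cell is also less guarded than restart after a milder event, because the second bullet sets no steroid threshold.

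**Working it through.** The main check is a comparison of texts.

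1. **First bullet against second bullet.** The first is an unconditional stop. The second is an instruction to restart after improvement and taper. It does not leave the decision to the PI, so it is not the PI-discretion exception found in other high-grade rows. The bullets are intact within one cell, so a broken table does not explain the conflict.

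2. **First bullet against last bullet.** The last bullet assumes a hold, which the first bullet does not provide for. The same sentence appears in the Grade 3 rash row of Table 3, where it fits because that row begins with a hold. The documents do not show how it came to be in the hypophysitis row.

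3. **Following every branch.** If the event resolves, the second bullet restarts the drug. If it does not, the last bullet stops the drug but its sub-bullet lets the PI resume. With all bullets applied, neither branch has to end in a final stop.

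4. **Cell against section text.** For Grade 4, the text of Section 6.1.1.4 agrees with the first bullet and disagrees with the second.

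5. **Recurrent events.** Table 4 sends these to the Grade 4 cell. The section text does not mention recurrence, so for a recurrent Grade 2 or 3 event there is no conflict with that text. The conflict is only between bullets of the cell.

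6. **Restart conditions.** The Grade 2 or 3 row has a 12-week limit and a prednisone ceiling of 10 mg/day. The Grade 4 restart bullet has neither. Section 6.1.1 supplies a general limit on holds for toxicity of 84 days (84/7 = 12 weeks), counted from the scheduled date of the delayed infusion. What is missing is therefore mainly the 10 mg/day ceiling.

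**How often this could matter.** Inputs: 2 cases in 2,616 patients (Section 6.1.1.4) and 45 participants (Section 13.1).

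- Rate = 2/2,616 = 0.000765, or 0.08%.
- Expected cases = 45 × 0.000765 = 0.034.
- Chance of at least one = 1 − (1 − 0.000765)^45 = 0.034, or 3.4%.
- The exact 95% interval for the rate is 0.0093% to 0.276%. This gives 0.004 to 0.124 expected cases and a 0.4% to 11.7% chance of at least one.

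These figures cover any grade. Grade 4 or recurrent cases would be fewer, and the documents give no separate rate for them.

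**The case against.** The strongest reply is that the cell opens with the stop and the section text agrees, so a careful prescriber would see the restart wording as a slip. Several safeguards also apply to this row. The first bullet requires that the PI be informed, and the cell calls for an endocrinology consult. Section 6.1 asks for a risk-benefit assessment before further dosing, and Section 6.1.1 ends treatment after a hold of more than 84 days. Section 5.5 requires immediate PI notification of life-threatening complications. Hypophysitis is an adverse event of special interest (Section 7.1.3.1) with one-business-day reporting (Section 7.5). All of this stands. It lowers the risk of unnoticed re-dosing, but it does not say which instruction holds.

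A reader might infer more than the documents support, in three ways:

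- **That prescribers would re-dose.** The cell is contradictory, and re-dosing would go against its own first bullet; for Grade 4 it would also go against the section text. The documents support could, not would.
- **That the section text bars re-dosing after recurrent hypophysitis.** It addresses Grade 4 only.
- **That the toxicity rules of Section 6.1 conflict with the organ tables in a way that needs general repair.** Section 6.1 says "The primary approach to Grade 1 to 2 irAEs is supportive and symptomatic care with continued treatment with atezolizumab", whereas the colitis, hypophysitis, pneumonitis and eye rows hold the drug at Grade 2, the liver row does so if Grade 2 persists beyond 5 days, and myocarditis of any grade stops it. But that sentence describes a primary approach, and Section 6 and most organ sections direct sites to the tables. This is mostly ordinary general-versus-specific drafting. The PI exceptions in the rash, eye and liver rows follow an opening permanent stop. Whether they need further resolution conditions is a clinical choice, and the symptomatic row of Table 6 already states one.

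**Conclusion.** The point holds for one table cell. For Grade 4 hypophysitis, the cell contradicts itself and its restart bullet contradicts the section text. For recurrent Grade 2 or 3 events sent to that cell, the contradiction is internal to it.

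The likely frequency is very low: about 0.03 any-grade cases among 45 participants, assuming the single-agent rate applies to atezolizumab given with stereotactic radiation. No endpoint, sample size, alpha or power figure depends on the cell. It should be corrected because it gives a wrong safety instruction for a severe event and the repair is simple.

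**What to change.** In the Grade 4 hypophysitis row, end the second bullet at the taper by removing the restart words. Delete the last bullet together with its PI sub-bullet. The row then matches the text of Section 6.1.1.4 and gives recurrent events a single instruction.

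If the medical team wants a PI exception, state it once in the row with conditions: Grade 1 or better within 12 weeks, and prednisone 10 mg/day or less, in line with the Grade 2 or 3 row. Amend the section text to match.

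Optionally, add one sentence to Section 6.1 saying that the organ tables and the myocarditis rule prevail over its general sentences on Grade 1 to 2 and life-threatening events. The rash, eye and liver rows need no change on this account.

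The cost is one corrected cell, and at most one added sentence or a matching text edit, in a single amendment. There is no statistical cost and almost no operational cost.
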